13.0 DATA HANDLING, DATA MANAGEMENT, RECORD KEEPING

13.1 Source Documents

Source documents are original documents, data, and records (e.g., medical records, pharmacy dispensing records, recorded data from automated instruments, laboratory data) that are relevant to the clinical trial. The investigator or their designee will prepare and maintain adequate and accurate source documents. These documents are designed to record all observations and other pertinent data for each patient enrolled in this clinical trial. Source documents must be adequate to reconstruct all data transcribed onto the case report forms.

13.2 Data Capture Methods and Management

Data for this trial will be collected using City of Hope's electronic capture system that is compliant with 21 CFR Part 11.

Study personnel will enter data from source documents corresponding to a subject's visit into the protocol-specific electronic Case Report Form (eCRF).

13.3 Case Report Forms/Data Submission Schedule

Study personnel will enter data from source documents corresponding to a subject's visit into the protocol-specific electronic Case Report Form (eCRF) when the information corresponding to that visit is available.

The investigator is responsible for all information collected on subjects enrolled in this study. All data collected during the course of this study must be reviewed and verified for completeness and accuracy by the investigator. All case report forms must be completed by designated study personnel. The completed case report forms must be reviewed, signed and dated by the Investigator or designee in a timely fashion.

All data will be collected using electronic data collection, stored as indicated in [Section 13.2](#), and will be submitted according to the timelines indicated in [Table 13.3](#).

Table 13.3 Data Submission Schedule

Form	Submission Timeline
Eligibility Checklist	Complete prior to registration
On Study Forms	Within 14 calendar days of registration
Baseline Assessment Forms	Within 14 calendar days of registration
Treatment Forms	Within 10 calendar days of treatment administration
Adverse Event Report Forms	Within 10 calendar days of AE assessment/notification
Response Assessment Forms	Within 10 calendar days of the response assessment
Other Assessment Forms (concomitant medications)	Within 10 calendar days of the assessment
Off Treatment/Off Study Forms	Within 10 calendar days of end of treatment/study
Follow up/Survival Forms	Within 14 calendar days of the follow up activity

13.4 Regulatory Records

The investigator will maintain regulatory records, including updating records in accordance with Good Clinical Practice guidelines and FDA regulations.

14.0 REPORTING OF ADVERSE EVENTS, UNANTICIPATED PROBLEMS & OTHER EVENTS OF INTEREST

The research team is responsible for classifying adverse events (AEs) and unanticipated problems (UPs) as defined in the relevant regulations and reporting to all applicable parties, including but not limited to the COH IRB, DSMC, Food and Drug Administration (FDA), National Institutes of Health (NIH) and other collaborators, e.g., pharmaceutical companies. The research team is responsible for the continued monitoring and tracking of all AEs in order to ensure non-reportable events are reviewed and monitored and do not rise to a reporting level.

14.1 Assessment of Adverse Events

The site Investigator will be responsible for determining the event name, and assessing the severity (i.e., grade), expectedness, and attribution of all adverse events as applicable per the [City of Hope Clinical Research Adverse Event and Unanticipated Problem policy](#). Adverse events will be characterized using the descriptions and grading scales found in NCI CTCAE v5.0. A copy of the scale can be found at:

https://ctep.cancer.gov/protocoldevelopment/electronic_applications/ctc.htm.

The following definitions will be used to determine the causality (attribution) of the event to the study agent or study procedure.

- **Unrelated** – The event is clearly NOT related to study treatment, and is clearly related to other factors such as the participant's clinical state, other therapeutic interventions, or concomitant medications administered to the participant.
- **Unlikely** – The event is unlikely related to the study treatment, and is most likely related to other factors such as the participant's clinical state, other therapeutic interventions, or concomitant drugs.
- **Possible** – The event may be related to study treatment, as it follows a reasonable temporal sequence from the time of drug administration, but could have been produced by other factors such as the participant's clinical state, other therapeutic interventions, or concomitant drugs.
- **Probable** – The event is most likely related to the study treatment, as it follows a reasonable temporal sequence from the time of drug administration and a known response pattern to the study drug, and is unlikely related to the participant's clinical state, other therapeutic interventions, or concomitant drugs.
- **Definite** – The event is clearly related to the study treatment, as it follows a reasonable temporal sequence from the time of drug administration and a known response pattern to the study drug, and is not reasonably explained by other factors such as the participant's condition, therapeutic interventions, or concomitant drugs.

14.2 Routine AE Collection and Reporting Guidelines

AEs will be collected from the signing of informed consent until ending study participation. Routine AE reporting will occur via data entry into the study eCRF. Adverse events will be monitored by the Protocol Management Team (PMT). Adverse events that do not meet the criteria of serious OR are not unanticipated problems do not require expedited reporting. AEs reported through expedited processes (e.g., reported to the IRB, DSMC, FDA, etc.) must also be reported in routine study data submissions.

Routing AEs recorded in the CRF will include:

During protocol treatment through EOT, all grade 2 or higher adverse events

All SAEs

14.3 Expedited Reporting

The table below indicates what events to report to expeditiously (Table 14.3).

Table 14.3 Expedited Reporting Guidelines

Time point	What to report
From signing of the consent to study completion	
• All UPs and AEs that meet the definition of a UP
For the time period beginning at treatment through 90 days following cessation of treatment, or 30 days following cessation of treatment if the subject initiates new anticancer therapy, whichever is earlier	
• All SAEs regardless of relationship to protocol therapy• All AESIs, overdose• AESIs (Section 14.2)- irAEs, overdose

All reportable events will require follow up until stabilization or resolution per the agreement of the Study PI.	
From Day 1 of protocol therapy up to 90 days post-last leflunomide dose	
• Pregnancies and lactation
Post Safety follow-up to removal from study	
• All SAEs that are at least possibly related to leflunomide.
NOTE: All events reported expeditiously require follow-up reporting until the event is resolved, stabilized, or determined to be irreversible by the investigator.	

14.3.1 Expedited reporting guidelines

Serious Adverse Events that require expedited reporting and unanticipated problems will be reported according to the approved [City of Hope Clinical Research Adverse Event and Unanticipated Problem policy](#). This includes all SAEs and UPs that meet COH DSMC/IRB expedited reporting criteria that occurred at COH and non-COH sites. For non-COH sites, the DCC will be responsible for reporting (see section 14.5.2).

14.4 Adverse Events of Special Interest (AESI) Requiring Expedited Reporting

14.4.1 Definition of Overdose

On a per dose basis, an overdose is defined as the following amount over the protocol-specified dose of lenalidomide assigned to a given patient, regardless of any associated adverse events or sequelae.

PO any amount over 60 mg leflunomide

On a schedule or frequency basis, an overdose is defined as anything more frequent than the protocol required schedule or frequency.

Complete data about drug administration, including any overdose, regardless of whether the overdose was accidental or intentional, should be reported.

14.4.2 Second Malignancies

A secondary malignancy is a cancer caused by treatment for a previous malignancy (e.g., treatment with investigational agent/intervention, radiation or chemotherapy). A secondary malignancy is not considered a metastasis of the initial neoplasm.

The investigator must immediately notify the Study PI/ DCC via an expedited report.

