2.0 BACKGROUND

2.1 Introduction/Rationale for Development

The term “CD30+ T-cell lymphoproliferative disorders” (CD30+LYPDs) describes a group of diverse diseases of the skin.[1] Primary cutaneous CD30+ T cell lymphoproliferative disorders (pcCD30+ T cell LPDs) are the second most common type of cutaneous T cell lymphomas (CTCL), after mycosis fungoides (MF), accounting for 30% of all primary cutaneous lymphomas [2, 3]. CD30+LYPD includes primary cutaneous anaplastic large cell lymphoma (pCALCL) and lymphomatoid papulosis (LyP). Their diagnostic hallmark is CD30 expression by the atypical lymphocytes, in the same typical membranous and golgi pattern observed in systemic anaplastic large cell lymphoma (sALCL) [4]. The treatment and prognosis of cutaneous CD30+ T cell LPDs differ significantly from those of systemic lymphomas, emphasizing the importance of a clinical pathological correlation and thorough workup to ensure an accurate diagnosis [5].

For both LyP and pcALCL, treatments are determined by the extent of disease. In LyP, topical treatments such as corticosteroids and nitrogen mustard are not effective in changing the overall course of disease. Current therapies treat only current existing lesions and associated symptoms, such as pruritus [6, 7]. Patients with diffuse disease are treated with phototherapy or methotrexate [8]. Both therapies cannot be continued indefinitely due to the risk of long term side effects. Once these therapies are discontinued, lesions usually recur with the same intensity. In pcALCL, for single or localized lesions the main effective treatments are surgical excision or radiotherapy. For multifocal or recurrent pcALCL, systemic therapies are used such as methotrexate, bexarotene or Brentuximab Vedotin [9]. Treatment decision making is particularly challenging, given the toxic nature of available agents for a relatively indolent lymphoma.

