6.0 ANTICIPATED ADVERSE EVENT LIST

6.1 Leflunomide

Per the package insert for leflunomide, the expected toxicities for leflunomide follow, where the asterisk (*) signifies a common event (10%-30% of patients), unmarked items are infrequent events (1-3% of patients), a double asterisk (**) signifies a rare but possibly serious event, and a triple asterisk (***) signifies an event that may become serious and occurs in up to 10% of patients:

Blood and lymphatic system	anemia (including iron deficiency anemia), ecchymosis, pancytopenia**, agranulocytosis**, neutropenia**, thrombocytopenia**, leukopenia**
Cardiac	angina pectoris, migraine, palpitation, tachycardia, vasodilatation

Endocrine	diabetes mellitus, hyperthyroidism
Eye	blurred vision, cataract, conjunctivitis, eye disorder
Gastrointestinal	diarrhea*, abdominal pain, dyspepsia, nausea, vomiting, oral ulceration, anorexia, pancreatitis**, constipation, esophagitis, flatulence, gastritis, gingivitis, melena, oral moniliasis, pharyngitis, salivary gland enlarged, stomatitis (or aphthous stomatitis), tooth disorder
Hepatobiliary	cirrhosis**, hepatitis**, hepatic failure**, acute hepatic necrosis**, cholelithiasis**, cholestasis**, elevated hepatic enzymes (primarily ALT and AST)
Immune system	allergic reactions, anaphylactoid reactions**
Infections	respiratory infection*, infections (including bronchitis, rhinitis, sinusitis, pharyngitis, pneumonia, and urinary tract infections, oral or vaginal candidiasis, herpes simplex, herpes zoster, and fungal dermatitis), opportunistic and/or severe infections** including sepsis, that may be fatal (especially Pneumocystis jiroveci pneumonia, tuberculosis, aspergillosis)
Metabolism and nutrition	hyperglycemia, creatine phosphokinase increased, hyperlipidemia
Musculoskeletal and connective tissue	arthrosis, bone necrosis, bone pain, bursitis, muscle cramps, myalgia, tendon rupture
Neoplasms	secondary malignancy**, cyst
Nervous system	headache*, peripheral neuropathy* (including peripheral numbness, tingling, burning, severe pain, cold sensation in the distal extremities, or extremity weakness), paresthesias, taste perversion (dysgeusia), anxiety, depression, dry mouth, insomnia, neuralgia, neuritis, sleep disorder, sweating increased, vertigo, migraine

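### Entry to the second-malignancy AESI depends on an undefined causal judgement, and new cancers that are not SAEs or that arise after the safety window can be missed

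*Combined protocol and SAP*

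**What the plan says.** Section 14.4.2 of the combined protocol and SAP gives this definition: "A secondary malignancy is a cancer caused by treatment for a previous malignancy". Its examples of such treatment are "e.g., treatment with investigational agent/intervention, radiation or chemotherapy", so leflunomide is covered. It states one exclusion: "A secondary malignancy is not considered a metastasis of the initial neoplasm". When the definition is met, "The investigator must immediately notify the Study PI/ DCC via an expedited report". That section sets no time limit.

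On who judges, Section 14.1 says: "The site Investigator will be responsible for determining the event name, and assessing the severity (i.e., grade), expectedness, and attribution of all adverse events". Its scale has five levels, from unrelated to definite, and concerns the study agent or study procedure.

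Table 14.3 sets the expedited rules. From the start of treatment until 90 days after it stops (30 days if new anticancer therapy begins, whichever is earlier) the list includes "All SAEs regardless of relationship to protocol therapy" and AESIs. From then until removal from study it lists only SAEs at least possibly related to leflunomide. Unanticipated problems (UPs) are reportable throughout.

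Section 14.2 collects adverse events until participation ends. It puts on the case report form those of grade 2 or higher through end of treatment (EOT), and all SAEs. The Study Calendar in Section 10.0 shows no adverse event assessment in the Active Follow-Up column. Its footnote p closes recording at the EOT Day 30 visit, apart from following earlier serious events to resolution. Active follow-up runs for 12 months (Section 5.7).

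Under neoplasms, Section 6.1 lists "secondary malignancy, cyst", with the first item marked as rare but possibly serious.

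**The concern.** The heading of 14.4.2 suggests a category for new cancers, but the text admits a cancer only after someone has judged that treatment caused it. Whether leflunomide raises the risk of cancer is a question that safety data should inform, so causation is better recorded after a case is captured than used to decide whether it is captured.

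The threshold is also undefined. Two investigators who both rate a cancer as possibly related could classify it differently and both comply. The 14.1 scale does not map onto the definition either. It rates relation to the study treatment, whereas 14.4.2 also counts cancers caused by earlier radiation or chemotherapy.

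At stake is complete capture of a risk that the protocol itself lists for an immunosuppressive drug, in a trial whose rationale appeals to a favorable toxicity profile.

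**Working it through.** **1. Which rule catches a new cancer**

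| New cancer | Expedited? | Recorded on the case report form? |
|---|---|---|
| SAE, on treatment or in safety window | Yes, any attribution (Table 14.3) | Yes (14.2) |
| Not an SAE, through EOT | Only if it meets 14.4.2 or is a UP | Yes if grade 2 or higher (14.2) |
| Not an SAE, after EOT but in safety window | Only if it meets 14.4.2 or is a UP | Not on the 14.2 list |
| SAE, after safety window, at least possibly related | Yes (Table 14.3) | Yes by 14.2; recording closed by footnote p |
| SAE, after safety window, unlikely or unrelated | Not by the SAE rule; only as a UP, or under 14.4.2 if blamed on earlier treatment | Yes by 14.2; recording closed by footnote p |
| Not an SAE, after safety window | Only as a UP, or under 14.4.2 if read without a time limit | Not on the 14.2 list |

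The documents contain no SAE definition; 14.1 and 14.3.1 refer to an institutional policy. How many new cancers could fall in the non-SAE rows therefore cannot be determined from them.

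**2. The cross-reference.** One line of the Table 14.3 safety-window row covers all AESIs. The next cites Section 14.2 as their source and names irAEs and overdose. The AESIs are defined in 14.4, which contains overdose and second malignancies and no irAEs.

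**3. What one case can show.** The plan's only adverse event detection figure (Section 12.2) is at least 86% for a true incidence of 15% in 12 patients. Check: 1 − 0.85^12 = 0.858, which agrees after rounding.

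For one observed case the exact (Clopper-Pearson) 95% limits are the 0.025 quantile of Beta(1, n) and the 0.975 quantile of Beta(2, n − 1):

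- n = 12: 1/12 = 8.3%, interval 0.2% to 38.5%
- n = 14: 1/14 = 7.1%, interval 0.2% to 33.9%

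There is no control arm, and every patient has had at least one earlier line of therapy (inclusion criterion 6). Nothing at this size separates a leflunomide effect from background or from earlier treatment.

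**4. Expected numbers.** The documents give no malignancy rate. Assume 1 to 3 new cancers per 100 patient-years.

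- Upper bound on exposure: 14 patients × 2 years = 28 patient-years. It is an upper bound because patients who progress leave the study (Section 5.8).
- Expected cases: 28 × 0.01 = 0.28 to 28 × 0.03 = 0.84.
- Chance of at least one (Poisson): 1 − exp(−0.28) = 24% to 1 − exp(−0.84) = 57%.
- Share of a nominal 24 months inside the safety window: (12 + 3)/24 = 62.5%, or (12 + 1)/24 = 54% if new anticancer therapy starts.
- After a 90-day window: 14 × 9/12 = 10.5 patient-years, so 0.11 to 0.32 expected cases.
- After recording closes under footnote p (about 1 month after treatment): 14 × 11/12 = 12.8 patient-years, so 0.13 to 0.39 expected cases.

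**The case against.** The strongest reply is that 14.4.2 governs one expedited category and little else. Inside the safety window any new cancer classed as an SAE is expedited whatever the attribution, and 14.2 records all SAEs with no causal condition. Section 12.4 summarises observed toxicities by type, grade, onset, duration and attribution, and plans no AESI table that the definition could bias. The expected numbers are a fraction of a case and rest on an assumed rate. All of this stands, and it rules out several stronger readings:

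- **That new cancers go unreported, or that their overall count is filtered by opinion.** The SAE rules in 14.2 and Table 14.3 operate independently of 14.4.2.
- **That the AESI requires certainty about causation.** No attribution level is named. A cancer rated possible might or might not qualify.
- **That the condition of a previous malignancy does not fit the enrolled disease.** Section 2.1 does say that the disease term "describes a group of diverse diseases of the skin". It then places these disorders among the cutaneous T-cell lymphomas and includes lymphomatoid papulosis in the group.

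It can also be said that 14.4.2 has no time limit, so the Table 14.3 window need not confine it. That helps only cancers already judged to be caused by treatment. It does nothing for a late cancer judged unrelated.

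The reply leaves two things unanswered: the undefined causal entry condition, and the combination of a narrower late SAE rule, no scheduled adverse event assessment in Active Follow-Up, and a footnote that closes recording while 14.2 keeps it open.

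**Conclusion.** The point holds as a minor one. Entry to the second-malignancy AESI depends on a causal judgement that the section does not tie to any attribution level and that one case in this trial cannot support. The practical gap is confined to new cancers not classed as SAEs and to cancers after the safety window.

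At an assumed 1 to 3 per 100 patient-years, fewer than one case is expected in the whole trial, and about 0.1 to 0.3 after a 90-day window. Of those late cases, the SAE rule in Table 14.3 would fail to expedite only those not classed as SAEs or rated below possible. The size rests on the assumed rate and on every patient completing 24 months, so it is an upper bound for each assumed rate. How many new cancers would not be SAEs or UPs depends on an institutional policy outside the documents. The primary endpoint, the sample size and the planned analyses are unaffected.

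**What to change.** 1. Reword 14.4.2 so that the AESI is any new malignancy, other than progression or metastasis of the study disease, arising from the first dose of leflunomide until removal from study, regardless of attribution.
2. Record attribution as a separate field on the 14.1 scale.
3. Ask about new malignancy at the 3-month visits already scheduled in Active Follow-Up, and mark this in the Study Calendar.
4. Correct the AESI line of Table 14.3: cite 14.4, name second malignancies, define or remove irAEs, and give this AESI the period in item 1.
5. Reconcile calendar footnote p with 14.2 on when adverse event recording ends, at least for new malignancies.

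The cost is a reworded definition, one question at existing visits and two consistency edits. The downside is that an unrelated cancer will occasionally be reported.

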15.0 ADHERENCE TO THE PROTOCOL & REPORTING OF PROTOCOL DEVIATIONS

Deviations from the protocol should be avoided, except when necessary to eliminate immediate hazard(s) for the protection, safety, and well-being of a research participant. As a result of deviations, corrective actions are to be developed by the study staff and implemented promptly. All protocol deviations and planned protocol deviations will be reported in accordance with the [Clinical Research Protocol Deviation policy](#).

16.0 STUDY OVERSIGHT, QUALITY ASSURANCE, & DATA AND SAFETY MONITORING

16.1 All Investigator Responsibilities

An investigator is responsible for ensuring that an investigation is conducted according to the signed investigator statement, the investigational plan, and applicable regulations; for protecting the rights, safety, and welfare of subjects under the investigator's care; and for the control of drugs under investigation.

16.2 Study PI Responsibilities

The Study PI is responsible for the conduct of the clinical trial, including overseeing that sponsor responsibilities in accordance with federal regulations.

16.3 Protocol Management Team (PMT)

The PMT minimally consisting of the Study PI, collaborating investigators, research nurse, clinical research associate/coordinator, and the study biostatistician is responsible for ongoing monitoring of the data and safety of this study, including implementation of the stopping rules for safety/toxicity.

The PMT is recommended to meet (in person or via teleconference) to review study status. The meeting is a forum to discuss study related issues including accrual, SAE/AE/UPs experienced, study response, deviations/violations and study management issues. The appropriateness of further subject enrollment and the specific intervention for subsequent subject enrollment are addressed.

16.4 Auditing & Quality Assurance

Clinical site auditing is conducted to ensure that the rights of human subjects are protected, that the study is implemented in accordance with the protocol and regulatory requirements, and that the quality and integrity of study data and data collection methods are maintained. This trial will be audited by the City of Hope Office Office for Safety and Data Quality. Details of clinical site auditing are documented in the [City of Hope Institutional Data and Safety Monitoring Plan \(DSMP\)](#).

